## Abstract for IRB

**Background:** Exercise treadmill test (ETT) is frequently done, inexpensive, relatively safe investigation for diagnosis of ischemic heart disease and prediction of exercise capacity. Ischemic heart disease is increasing by leaps and bounds all over the world even in the developing countries like Bangladesh. The incidence rate of coronary artery disease is not limited to male gender as previously seen. As a cause of industrialization and increased life expectancy, incidence of ischemic heart disease in females is escalating now in Bangladesh also. Though ETT is a well accepted investigation to diagnose Coronary Artery Disease (CAD), it has a high false positive and false negative result if ST segment response alone is calculated for interpretation of the test.

**Rationale:** Duke Treadmill Score (DTS) and Simple Treadmill Score (STS) are valid and well known scores which can predict coronary artery disease burden more efficiently than ST segment response alone. Computer generated Cleveland clinic score (CCS) is another valid treadmill score which has a complex algorithm but effective way to predict 3 year and 5 year survivability. These three scores are well tested on western population but to our best knowledge there is little or no information regarding their predictability of CAD. It's well known that ETT has a high false positive result in our population, so applying the scores may render ETT more efficient and abrogate unwanted risk of undergoing coronary angiography to diagnose CAD, especially in females.

**Objective:** To identify difference of predictability of DTS, STS and CCS to diagnose significant CAD by Coronary Angiography (CAG).

**Method:** A Cross-Sectional study will be carried out on patients attending University Cardiac Center in Bangabandhu Sheikh Mujib Medical University (BSMMU) for stable chest pain to find out the accuracy of commonly applied treadmill scores (DTS, STS) and ST segment response to diagnose CAD as well as accuracy of computer generated Cleveland Clinic Score will be tested. Total 102 people including male and female who have undergone ETT will be included according to inclusion and exclusion criteria and informed written consent will be taken. Treadmill scores will be calculated. The patients who have undergone exercise treadmill test for provable ischemia and have their coronary angiogram done for confirmation and identification of coronary artery lesion according to the recommended guideline for CAG with-in 6 months will be selected. All available data will be analyzed using SPSS. The accuracy of different scores will be calculated and compared with each other. According to currently available data from studies in western population we predict the treadmill scores will have good predictability and will be efficient to control unwanted CAG procedure to diagnose CAD.

**Date:**

**Date:**

**Date:**

## IRB Check List for Study Population (List A)

(Please tick mark against your appropriate answers for all the statements below, write NA if not applicable)

1. Source of study population		7. Does the study require:	
a. Sick persons b. Healthy persons c. Minors or persons under guardianship	✓Yes / No Yes / ✓No Yes / ✓No	a. Use of records (hospital, medical, death, birth, lab reports, or others). b. Use of fetal tissue or abortus. c. Use of organs or body fluids(serum, blood, CSF, sputum, urine, stool, pus, tears, amniotic fluid etc).	Yes / ✓No Yes / ✓No Yes / ✓No
2. Age Groups of participants		8. Are subjects clearly informed about:	
a. 0-4 years b. 5-10 years c. 11-17 years d. 18-64 years e. 65+ years	Yes / ✓No Yes / ✓No Yes / ✓No ✓Yes / No ✓Yes / No	a. Nature and purpose of study. b. Procedures to be followed including alternatives used. c. Physical risks. d. Mental Risks. e. Private questions. f. Benefits to be derived.	✓Yes / No Yes / No ✓Yes / No Yes / ✓No ✓Yes / No
3. Gender Groups			
a. Male b. Female c. Transgender	✓Yes / No ✓Yes / No ✓Yes / No	g. Right to refuse to participate or to withdraw from the study. h. Confidential handling of data. i. Compensation (where there are risks or loss of working hours or privacy is involved in any particular procedure).	✓Yes / No ✓Yes / No Yes / ✓No
4. Does the study involve special groups as listed below ?		9. Signed informed consent form will be obtained from subjects before admission in to the study.	
a. Pregnant women b. Fetus in utero c. Prisoners d. Mentally impaired e. Sex workers/ drug addicts f. Refugee/ tribal groups	Yes / ✓No Yes / ✓No Yes / ✓No Yes / ✓No Yes / ✓No Yes / ✓No	a. From patients, if adults, >18 y b. From parents or guardians if patients are minors, < 18 y.	✓Yes / No Yes / No
5. Physical Risks:		10. Will precaution be taken to protect anonymity of subjects ?	✓Yes / No
a. Physical risks including venipuncture, x-ray, skin test d. Social risks e. Psychological risks f. Discomfort to subject g. Invasion of body h. Invasion of privacy i. Disclosure of information damaging to subjects or others	✓Yes / No Yes / ✓No Yes / ✓No ✓Yes / No ✓Yes / No ✓Yes / No ✓Yes / No ✓Yes / No ✓Yes / No	a. Human exposure to radiation ? b. Investigational new drug or device. c. Human exposure to infectious,toxic, and other harmful agents. d. New treatment regimen. e. Observation of public behavior.	✓Yes / No Yes / ✓No ✓Yes / No Yes / ✓No Yes / ✓No
5. Project/ study site		11. Does the study involve:	
a. BSMMU Hospital b. Urban Community c. Rural Community d. Other hospitals	✓Yes / No Yes / No Yes / No Yes / No	a. Healthy volunteers. b. Healthy control groups c. Untreated or 'placebo' groups. d. Invasive tests on healthy subjects to assess "normal" values in population.	Yes / ✓No Yes / ✓No Yes / ✓No Yes / No
		12. Does the study population require the following groups ?	
		a. Cross-sectional study b. Cohort, longitudinal study c. Controlled Clinical Trial	✓Yes / No Yes / ✓No Yes / ✓No

## IRB Check List B

### 1. Trial Registration

- (a) Has the trial been registered with any registration authority?  Yes /  No  
(b) If yes, please provide full information including registration number, date of registration, and organization.

a. Organization	name	&	address:
ClinicalTrials.gov PRS Protocol Registration and Results System			
b. Registration number:	NCT02879032	C. Date of Registration:	24 th August, 2016

### 2. Dissemination plan

Please describe the anticipated plan for disseminating the results of the study when completed.

Results will be presented as (check as many apply):

- a. Thesis
- b. Dissertation
- c. Journal publication
- d. Seminar at the university and international workshop/conference.
- e. Internal report
- f. CONSORT (Consolidated Standards for Reporting Trials) format has been included and will be followed in reporting the trial results when completed. This is required mostly for controlled clinical trials.

### 3. Conflicts of interests: Yes / No

If yes, please describe any conflicts of interests involved or anticipated in the study.

### 4. Investigator's Certification: Has the PI successfully completed the NIH clinical investigator's qualifying exam online? Yes / No

NIH Clinical Investigator Exam:

Completion date: 12th August, 2016

Certification obtained: NIH Office of Clinical Research Training and Medical Education computer-based Clinical Research Training course.

### 5. Expected Outcome: What will be the expected outcome of the study if successfully completed.

The study will be expected to: (Check as many apply).

- a. Generate new knowledge.
- b. Confirm existing knowledge.
- c. Extend current knowledge to wider field of application.
- d. Reassess known effects of an intervention on BD population.
- e. Provide basis for future, definitive studies.
- f. Change current diagnostic and therapeutic practice or procedures.
- g. Change current behavior among population.

## Budget

Instrument or Material	Unit	Unit Cost	Total estimated budget (In Taka)
1. Cost of investigations	102	11400	(1,162,800/=) Patients Self expenditure for ETT and CAG
2. Internal work, literature search and purchase of article or reference paper	-	-	15,000/=
3. Stationeries, Paper files, staplers etc	-	-	5000/=
4. Printing and reproduction	-	-	10,000/=
5. Thesis writing, computer compose etc	-	-	10,000/=
6. Thesis binding	-	-	1500/=
7. Miscellaneous	-	-	1000/=
TOTAL42,500/=			

## Introduction

At present several treadmill scores have been proposed as means for improving the diagnostic accuracy of the exercise treadmill test (ETT) and to predict future risk of cardiac events (Berman et al., 1978 & Do et al., 1997). Although a large number of noninvasive stress testing modalities are currently available, the exercise ECG is still used as a standard for comparison with other clinical and testing risk markers. It is also the least costly of all provocative noninvasive tests. The Duke Treadmill Score (DTS), traditionally a prognostic score, was recently tested as a diagnostic score and shown to predict CAD better than the ST response alone(Shaw et al., 1998). But questions remain regarding the diagnostic accuracy of treadmill scores when applied to a different patient population; furthermore, many treadmill scores have not been compared with one another in the same population(Fearon et al., 2002).To date, no composite stress-test score or noninvasive risk index has been shown to provide both accurate diagnostic and prognostic risk estimates. Despite that exercise treadmill test remains a useful test for diagnosing coronary artery disease (CAD) in patients with chest pain and at intermediate risk for CAD (Do et al., 1997).The sensitivity and specificity of ETT varies considerably. According to a meta-analysis conducted by Gianrossi et al there was a wide variability in sensitivity and specificity of ETT [sensitivity  $68\pm 16\%$  (range 23–100%); specificity  $77\pm 17\%$  (range: 17–100%). Another Meta analysis showed sensitivity of  $81\pm 12\%$  (range: 40–100%) and specificity of  $66\pm 16\%$  (range: 17–100%) (Myers et al., 1994).Fearon WF et al showed sensitivity and specificity was higher when treadmill scores were applied in comparison to ST response alone. They used a consensus score consisting of the Morise, Dentrano and VA score and found predictive accuracy of the consensus score for stratifying patients to low and high likelihood for CAD was significantly higher than the predictive accuracy of DTS, 80(74-86)% versus 71(65-77)% ( $p< 0.0001$ ). But Fearon WF et al conducted the study only on male population in USA and the consensus score was calculated by average of computer generated treadmill scores. In 2012 Mao L et al have shown 73 out of 104 male patients were detected CAD both by ETT and CAG, the accuracy rate was 70.2% which was much higher than that (50.0%) of the female patients ( $p<0.05$ ) and they only used ST changes alone to demonstrate ETT positivity In this study, we will compare the diagnostic accuracy of well known prognostic scores namely, Duke Treadmill Score, Simple Treadmill Score and Cleveland Clinic Score to identify significant coronary artery lesion in Bangladeshi male and female patients.

## Rationale

Though exercise treadmill test has high false positive and negative rates(Zang et al., 2007) , it is cheap, easily available, less time consuming to the interpret results and its accuracy can be increased by calculating ST/HR index, treadmill score, QT dispersion and so on (Kronander 2010 &Dentrano 1989). On the contrary the gold standard test coronary angiogram for detecting CAD is expensive, time consuming, potentially hazardous with many complications and often the CAG shows normal coronary arteries in female population. ST-segment depression and chest pain as the classic criteria for CAD diagnosis are well known and accepted. Besides If treadmill score were used the diagnostic accuracy of ETT would had been higher. The accuracy of different treadmill scores in Bangladeshi population especially the female population is largely unknown. Duke Treadmill Score and Simple Treadmill Score are well validated score in western population and are used for diagnostic & prognostic interpretation of ETT. The predictive accuracy of DTS to diagnose CAD is 71% (Fearon 2002). In 2001 Raxwal V et al. showed simple treadmill score has sensitivity of 88% and specificity of 96%. If we calculate the accuracy of simple treadmill score using the formula “Accuracy = (Sensitivity) x Prevalence + (Specificity) x (1- Prevalence)” it sums up nearly 93% according to prevalence of CAD in urban population. Cleveland Clinic Score is a prognostic score of ETT. It gives value from which we can predict the probability of 3 year or 5 year survival. It was shown that it has a very high negative predictive value approaching 97%. Besides to the best of our knowledge Cleveland Clinic Score was not tested as a diagnostic predictor of CAD and there are few studies regarding treadmill scores predictability in Bangladesh. In our study we will use all of these three scores and compare their accuracy to predict significant CAD. DTS, Simplified Treadmill Score, and Cleveland clinic score can be implemented effectively to identify patients with low probability of CAD and excluded from undergoing expensive and potentially hazardous CAG if the real scenario of the treadmill scores is known in our population.

## **Research question**

How do different treadmill scores (Duke Treadmill Score, Simple Treadmill Score, Cleveland Clinic Score) vary to predict probability of Coronary Artery Disease in Bangladeshi population in a tertiary care hospital?

## **General Objectives**

To identify difference of predictability of DTS, Simple Treadmill Score and Cleveland Clinic Score to diagnose significant CAD by Coronary Angiography.

## **Specific Objectives**

1. To estimate accuracy of ST segment response, DTS, Simple Treadmill Score and Cleveland Clinic Score to predict CAD.
2. To compare DTS, Simple treadmill score, Cleveland Clinic Score accuracy to predict coronary artery disease.
3. To identify the relation of different level of treadmill scores with severity of CAD.

## Literature Review

According to Islam AKMM and Majumder AAS “Coronary artery disease in Bangladesh: A review published in 2013 the exact prevalence of CAD in Bangladesh is not known. Only a limited number of small-scale epidemiological studies are available. Probably the prevalence of IHD was first reported in 1976, which was 0.33%. More recent data indicates CAD prevalence between 1.85% and 3.4% in rural and 19.6% in an urban sample of working professionals. Despite marked disparity in values, there seems to be a rising prevalence of CAD in Bangladesh.

Gianrossi et al. investigated the diagnostic accuracy of ETT through a meta-analysis including 147 published reports involving 24,074 patients who underwent both coronary angiography and ETT. There was a wide variability in sensitivity and specificity of ETT [sensitivity  $68 \pm 16\%$  (range 23–100%); specificity  $77 \pm 17\%$  (range: 17–100%)]. Another Meta analysis showed sensitivity of  $81 \pm 12\%$  (range: 40–100%) and specificity of  $66 \pm 16\%$  (range: 17–100%).

2014 Taimur et al evaluated ETT (Treadmill) Positive Patients in a Tertiary Care Hospital of Bangladesh by doing angiogram subsequently. They found the overall positive predictive value of ETT is 77.9%, and for male patient PPV is 86.25% and for female patient it is 50%.

In 1987 Mark DB et al showed Duke Treadmill Score was useful for stratifying prognosis in patients with suspected coronary artery disease who were referred for catheterization, and may provide a useful adjunct to clinical decision making in the larger population of patients being evaluated for chest pain. They had evaluated 2842 patients with chest pain who had both treadmill testing and cardiac catheterization.

Shaw LJ et al in 1998 estimated DTS provides accurate diagnostic and prognostic information for the evaluation of symptomatic patients evaluated for clinically suspected ischemic heart disease.

In 2015 Gunaydin et al showed there was a strong negative correlation between DTS and Syntax Score ( $r = -0.72$ ,  $p < 0.001$ ). The area under the receiver-operating curve of DTS was 0.83 (0.77-0.88,  $P < 0.001$ ) for predicting significant presence of CAD. The optimal cut-off value of DTS to predict the significant presence of CAD was -3.7 (sensitivity of

74% and a specificity of 73%). The area under the receiver-operating curve of DTS was 0.84 (0.78-0.90,  $P < 0.001$ ) for predicting high SS. The optimal cut-off value of DTS to predict high SS was -11.2 (sensitivity of 81% and a specificity of 80%). They concluded DTS can predict the presence and severity of stable coronary artery disease before coronary angiography and may enable to estimate revascularization method that will be required after the procedure.

In 2002 a simple score was developed for use specifically in women by Morise AP et al. For the validation group, score ranges are shown with the prevalence of CAD:  $<20 = 0/5$  or 0%,  $20-29 = 3/26$  or 11%,  $30-39 = 20/56$  or 36%,  $40-49 = 33/81$  or 41%,  $50-59 = 24/49$  or 49%,  $60-69 = 22/32$  or 69%, and  $>70 = 7/7$  or 100%.

In 1998 Alexander KP et al determined the ability of a treadmill score to provide accurate diagnostic and prognostic risk estimates in women. They estimated the diagnostic and prognostic value of the DTS in 976 women and 2,249 men who underwent both treadmill testing and cardiac catheterization in a single institution from 1984 to 1994. Results. Women and men differed significantly in DTS (1.6 vs. -0.3,  $p < 0.0001$ ), disease prevalence (32% vs. 72% significant coronary artery disease [CAD],  $p < 0.001$ ), and 2-year mortality (1.9% vs. 4.9%,  $p < 0.0001$ ). Although overall women had better survival, the DTS performed equally well in stratifying both genders into prognostic categories. The DTS actually performed better in women than in men for excluding disease.

## **Materials and Methods**

### **Study design**

Type of study: Cross sectional study

As we want to correlate the different treadmills scores and identify which one is better to predict coronary artery disease in male and female population, cross sectional study is good one. By this study design we can find the different treadmill scores and angiographic data within a short time, easily and with less cost.

### **Study Area**

University Cardiac Center, Bangabandhu Sheikh Mujib Medical University (BSMMU).

BSMMU is a renowned institute in Bangladesh with good indoor and outdoor facility. It also has good inpatient and outpatient services for local and other patients coming from distant places. There is a good mix of male and female patients also which is needed to test the study hypothesis. Overall, the patients coming in outdoor facility to get treatment represent the Bangladeshi population very well and uniformly.

**Period of study:** November 2016 to November 2017 (One year).

**Study population:** All stable patients visited University Cardiac Center, Bangabandhu Sheikh Mujib Medical University (BSMMU) for evaluation of stable chest pain.

### **Sampling Procedures**

Patient presented with stable chest pain, who have undergone ETT according to Bruce protocol and admitted for CAG, will be selected as case considering inclusion and exclusion criteria. Detailed and thorough clinical assessment will be done and recorded. All available previous medical documents will be checked meticulously. Patients with previous revascularization, left bundle-branch block, paced rhythms or Wolff-Parkinson-White syndrome (WPW) on resting electrocardiogram (ECG), or valvular heart disease, congenital heart disease will be excluded from the study. To avoid falsely increasing the accuracy of the exercise treadmill test, patients with a previous myocardial infarction by history or by diagnostic Q wave will be excluded.

With history, clinical findings and investigations cases other than stable chest pain will be excluded. Informed written consent will be taken from the patient. CAG report will be collected from the Cath lab after the procedure.

### **Inclusion criteria:**

1. Male and female patients undergone CAG and ETT within 6 months interval for stable angina.
2. Age between 30-69 years (Gibbons et al., 2002).

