## **Procedures during study**

### **Exercise Treadmill Testing**

Patients will be undergoing treadmill testing using Bruce treadmill protocol. Before treadmill testing, the patients will be given a questionnaire. This questionnaire will estimate the patient's exercise capacity before the test and thus will allow most patients to reach maximal exercise capacity (Myers 1994). Visual ST-segment deviation will be measured at the J junction and will be corrected for pre-exercise ST-segment depression while standing; ST slope will be measured over the following 80 ms and will be classified as up sloping, horizontal, or down sloping. Slope will be coded as 1 horizontal, down sloping, or upsloping ST depression and 0 for normal slope (up sloping  $<2$  mm or ST-segment depression of  $<0.5$  mm). The ST response will be considered which has the most horizontal, downsloping or up sloping ST-segment depression in any lead, except aVR, during exercise or recovery. An abnormal response will be defined as  $\geq 1$  mm of horizontal or downsloping or  $\geq 2$  mm upsloping ST-segment depression (Griffin 2013). The exercise tests will be analyzed, and reported per standard protocol and manual calculation. Decision for cardiac catheterization will be consistent with clinical practice. Analyses will be performed with the investigators blinded to clinical and angiographic results.

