**Fig: Cleveland Clinic Score Nomogram.**

## Appendix B

### Study design flow chart:

**Patient with Stable chest pain who underwent ETT and admitted for CAG**

**Patient selected according to Inclusion and exclusion criteria**

**DTS, Simple Treadmill Score, Cleveland Clinic score calculated**

**Report collection after CAG**

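### The inclusion criterion and abstract require an angiogram already done, the sampling text and flow chart enrol before it, and no consecutive-enrolment rule is set, so the criterion and abstract allow selection with both results known

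*Combined protocol and SAP*

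**What the plan says.** The combined protocol and SAP describes the point of enrolment in two ways.

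- **CAG already done.** Inclusion criterion 1 reads "Male and female patients undergone CAG and ETT within 6 months interval for stable angina". The Method paragraph of the Abstract for IRB says that the patients to be selected are those who have undergone ETT and "have their coronary angiogram done for confirmation and identification of coronary artery lesion", within 6 months.
- **CAG still to come.** Sampling Procedures takes patients "who have undergone ETT according to Bruce protocol and admitted for CAG, will be selected as case considering inclusion and exclusion criteria", and then states that "CAG report will be collected from the Cath lab after the procedure". The Appendix B flow chart starts from "Patient with Stable chest pain who underwent ETT and admitted for CAG". It then applies the criteria, calculates the three scores and collects the report last.

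On how patients are drawn from those eligible, Sampling Procedures gives no consecutive, random or all-comers rule and no log of eligible patients not enrolled. The phrase "All stable patients visited University Cardiac Center" appears under Study Area, where it defines the study population and not the sampling.

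The only blinding statement is in the Exercise Treadmill Testing section: "Analyses will be performed with the investigators blinded to clinical and angiographic results".

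**The concern.** In a diagnostic accuracy study, enrolment should not depend on whether the index test and the reference test agree. Criterion 1, taken as written, is met only once CAG has been done, so a site applying it literally enrols when the reference result may already be known. With no consecutive rule, patients whose ETT and angiogram disagree can be passed over, deliberately or not. Patients never recorded cannot be recovered in the analysis.

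This concerns who enters the sample. It is separate from blinded reading of the tests and from the clinical decision to refer for CAG. It also bears on an aim the protocol itself states: Sampling Procedures excludes prior infarction so that ETT accuracy is not overstated.

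**Working it through.** **1. The plan's own figure.** The Sample size calculation section uses p1 = 0.71 (Duke Treadmill Score accuracy), p = 0.55, Zα = 1.96 and Zβ = 1.28:

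n = [1.28·√(0.55·0.45) + 1.96·√(0.71·0.29)]² / (0.55 − 0.71)² = 90.98, so 91.

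91 × 1.11 = 101.01, rounded up to 102. Both stated figures reproduce, and this point disputes neither.

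**2. The texts side by side.**

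| Place | State of CAG at selection | Results that can be known at selection |
|---|---|---|
| Abstract for IRB, Method | done | ETT and CAG |
| Inclusion criterion 1 | done | ETT and CAG |
| Sampling Procedures | patient admitted for it | ETT only |
| Appendix B flow chart | patient admitted for it; report collected last | ETT only |

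Sampling Procedures selects patients by applying the inclusion and exclusion criteria, so it brings in the criterion it conflicts with. Criterion 1 also does not say that ETT must precede CAG. The Exercise Treadmill Testing section adds a third timing, because it describes the treadmill test itself as still to be done.

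**3. Size, for one score.** Let the true accuracy be 0.71, the plan's value, and let f be the fraction of patients discordant between that score and CAG who are passed over. The documents give no value for f, so the values below are assumptions.

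Apparent accuracy = 0.71 / [0.71 + 0.29(1 − f)]

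Patients passed over to enrol 102 = 0.29·f × 102 / [0.71 + 0.29(1 − f)]

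| f (assumed) | Denominator | Apparent accuracy | Excess over 0.71 | Passed over |
|---|---|---|---|---|
| 10% | 0.971 | 0.731 | 0.021 | about 3 |
| 20% | 0.942 | 0.754 | 0.044 | about 6 |
| 30% | 0.913 | 0.778 | 0.068 | about 10 |
| 50% | 0.855 | 0.830 | 0.120 | about 17 |

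**4. Comparison with random error.** The 95% half-width for an accuracy of 0.71 with 102 patients is 1.96·√(0.71·0.29/102) = 0.088. On this model the bias equals that half-width when f is a little under 40%.

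**5. What the model leaves out.** It treats one score and one accuracy figure. It does not estimate the effect on an AUC or on a difference between two scores.

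**The case against.** The strongest reply is that the conflict is partly one of reading. Criterion 1 can be taken to state which tests an analysed patient must have and how far apart, not when enrolment occurs. The two texts that do describe enrolment, Sampling Procedures and the flow chart, agree with each other and already place selection and scoring before the CAG report is collected. The IRB check list (List A) also requires signed consent before entry to the study, and its item on use of records appears ticked No, which points away from retrospective filling.

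Part of this stands. The pre-CAG order is already in the plan, so the fix is mainly alignment. But the abstract links a completed angiogram to being selected, which the lenient reading does not explain. Consent before study entry can still come after CAG. The records tick carries little weight, since Sampling Procedures itself reviews previous medical documents and collects the cath lab report. The blinding sentence covers analyses, not the choice of patients.

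Three stronger readings are tempting and are not supported:

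- **That selective enrolment is intended or will occur.** Nothing in the documents shows this, and the reason given for excluding prior infarction suggests the opposite intent.
- **That every score's accuracy and AUC would be inflated.** A patient discordant on one measure may be concordant on another. In the flow chart, scores are calculated after selection, so passing over patients on a score would require working it out earlier. Because the scores are compared in the same patients, a common bias would partly cancel in the differences.
- **That the principal investigator's role in data collection shows who chooses the patients.** The Quality assurance strategy paragraph speaks of about a month of data collection followed by editing of the questions. In a one-year study that reads as piloting the questionnaire, and it does not say who selects patients.

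**Conclusion.** The point holds as an inconsistency with a foreseeable consequence. Two places make a completed angiogram part of eligibility, two place enrolment before it, and no section requires consecutive enrolment. Under the criterion and abstract wording, patients can be chosen with both results known. Under Sampling Procedures and the flow chart alone, only the ETT result is known at selection.

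The possible effect is an upward bias in the apparent accuracy of the ST response and of scores that share the ETT findings, by differing amounts. Appendix A shows ST deviation entering the Duke score with a multiplier of 5 and ST depression entering the Simple Treadmill Score. For the Cleveland Clinic Score the available text does not show the components.

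The shift from 71% to 75% or 83% is a single-score illustration. It rests on the planning accuracy and on assumed fractions of 20% and 50%; it does not forecast this study's bias. The change should be made, because the present wording permits result-dependent sampling and the remedy is cheap.

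**What to change.** 1. Reword inclusion criterion 1 and the Method paragraph of the abstract to: admitted for CAG, with ETT done within the preceding 6 months. This also settles the order of the two tests.
2. In Sampling Procedures, state that all consecutive eligible admissions are approached, and that those consenting are enrolled and scored before CAG, until 102 are reached.
3. Keep and report a short log of eligible patients not enrolled, giving sex, ETT result and reason.

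The cost is a few sentences and a one-page log. The sample size and the tests performed do not change. The downside is that the sample can no longer be filled retrospectively from patients whose angiogram is already done.
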